**Appendix F. ICD-10-CM and CPT Procedure Codes to Identify Outcomes: Stillbirth**

ICD-10-CM diagnosis or CPT procedure codes	Description of codes
O36.4	Maternal care for intrauterine death
Z37.1	Single stillbirth
Z37.3	Twins, one live born and one stillborn
Z37.4	Twins, both stillborn
Z37.6	Other multiple births, some live born
Z37.7	Other multiple births, all stillborn

**Appendix G. ICD-10-CM and CPT Procedure Codes to Identify Outcomes:  
Small-for-gestational age**

ICD-10-CM diagnosis or CPT procedure codes	Description of codes
P05.1x	Newborn small for gestational age
P05.x	Newborn light for gestational age
P07.0x	Extremely low birth weight newborn
P07.1x	Other low birth weight newborn

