###### *Secondary:*

Pregnancies ending in spontaneous abortion, defined as spontaneous losses before 20 weeks of gestation, and identified using ICD-10-CM diagnosis and procedure codes.

Pregnancies ending in stillbirth, defined as *in utero* fetal deaths 20 weeks of gestation and after, and identified using ICD-10-CM diagnosis and procedure codes.

Small-for-gestational age in live-born infants, defined as birth weight 10th percentile, and identified using ICD-10-CM diagnosis codes.

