#### **9.3.2.2 Secondary outcomes**

Spontaneous abortion is defined as loss of the embryo or fetus between conception and the point at which the death would be considered a stillbirth, at week 20 or later ([Likis et al, 2013](#)). In the MarketScan CCE database and the HIRD, spontaneous abortion will be identified through ICD-10-CM diagnostic codes and procedure codes (see [Appendix E](#) for codes).

Stillbirth is generally defined as intrauterine fetal death on or after the 20th week of gestation, of a fetus weighing 350 grams or more ([Likis et al, 2013](#)). Although the date of fetal death may not be known, stillbirth is more likely than spontaneous

abortion to be medically attended, and will be identified through ICD-10-CM diagnostic codes and procedure codes in the MarketScan CCE database and the HIRD (see [Appendix F](#) for codes).

Small-for-gestational age in live born (LB) infants, defined as birth weight 10th percentile, will be identified using ICD-10-CM codes in the MarketScan CCE database and the HIRD (see [Appendix G](#) for codes).

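### The small-for-gestational-age code list includes low-birth-weight codes that ignore gestational age, so preterm infants of normal size for age can be counted as cases

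*Protocol*

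**What the plan says.** Section 9.3.2.2 gives the definition: "Small-for-gestational age in live born (LB) infants, defined as birth weight", followed by the 10th percentile (the comparison sign is not legible in the text at hand; I read it as below). The abstract in Section 4 says the same. The name of the outcome makes this a percentile for gestational age.

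On identification, Section 9.3.2.2 says the outcome "will be identified using ICD-10-CM codes in the MarketScan CCE database and the HIRD" and points to Appendix G. That appendix lists four code groups:

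- P05.1x, "Newborn small for gestational age"
- P05.x, "Newborn light for gestational age"
- P07.0x, "Extremely low birth weight newborn"
- P07.1x, "Other low birth weight newborn"

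Any listed code appears to suffice. No text requires a P07 code to occur with a P05 code, limits it to term births, or combines it with weeks of gestation.

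**The concern.** The first two code groups are described relative to gestational age, as the definition requires. The last two are described by weight alone. An infant born early can have a low weight that is normal for its age. Such an infant can carry a P07 code and be counted as SGA although it does not meet the definition.

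Two consequences follow. A real effect of erenumab on fetal growth is diluted by infants whose growth is unaffected. An effect on preterm birth alone could be reported as an effect on growth. Preterm birth is not itself among the outcomes in Section 8, so such an effect has no outcome of its own in which to appear.

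SGA is one of the four outcomes for which Section 7.3 plans to evaluate a null hypothesis, and Section 9.6.1.1 has outcome proportions reported annually. The misclassification would therefore affect the descriptive reports as well as any comparison.

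**Working it through.** **1. Does anything elsewhere in the protocol repair the list?**

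- Section 9.3.1.1 uses week-of-gestation codes (Z3A) to date the pregnancy, but does not apply them to SGA.
- Section 9.3.2.1 excludes prematurity-related conditions, but only from the malformation outcome.
- Section 9.3.4.1 plans chart validation for malformations, spontaneous abortion, stillbirth, LMP and the migraine algorithm. SGA is not included.
- Section 9.6.2.5.3 says that quantitative bias analyses, including for outcome misclassification, will be explored. It does not name SGA.
- Appendix D writes conditions into its code list where they are wanted (spina bifida only without the anencephaly codes; one hypospadias code excluded). Appendix G contains none.

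**2. Is there a stated figure to reproduce?** No. The protocol gives no rate, sample size or power for SGA. Table 2 concerns malformations only. Everything below rests on assumed inputs.

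**3. Formula.** Let w be the share of counted cases in the reference group that are not SGA. Counted cases are then a mixture:

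- Growth effect RR, no effect on the others: observed RR = (1 − w) × RR + w
- No growth effect, RR on preterm low birth weight: observed RR = (1 − w) + w × RR

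These are risk ratios for simplicity; the protocol's effect measure is the odds ratio.

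**4. First set of assumptions.** 5-8% of infants coded SGA; 3-6% low birth weight but not SGA.

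- Lowest share: w = 3/(8 + 3) = 27%
- Highest share: w = 6/(5 + 6) = 55%
- True growth RR of 1.5: (8 × 1.5 + 3)/11 = 1.36 and (5 × 1.5 + 6)/11 = 1.23
- RR of 1.5 on preterm low birth weight only: (8 + 3 × 1.5)/11 = 1.14 and (5 + 6 × 1.5)/11 = 1.27

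**5. Second, wider set, built from components.** True SGA 10%; low birth weight L = 6-10%; fraction of those preterm and not SGA f = 30-60%; capture by P07 codes c = 50-90%; sensitivity of P05 codes s = 20-100%; P05 and P07 coding independent.

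- False positives = L × f × c
- True positives = L(1 − f) × [1 − (1 − s)(1 − c)] + [0.10 − L(1 − f)] × s

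Low end (s = 1.0, L = 0.06, f = 0.3, c = 0.5): false positives 0.009, true positives 0.100, w = 0.009/0.109 = 8%.

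High end (s = 0.2, L = 0.10, f = 0.6, c = 0.9): false positives 0.054; true positives 0.04 × 0.92 + 0.06 × 0.2 = 0.0488; w = 0.054/0.1028 = 53%.

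Over the 72 combinations examined, w exceeds one half in 2.

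**6. Both sets together (w from 8% to 55%).**

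| w | true growth RR 1.5 appears as | false SGA RR if preterm low-birth-weight RR is 1.5 |
|---|---|---|
| 8% | 1.46 | 1.04 |
| 20% | 1.40 | 1.10 |
| 30% | 1.35 | 1.15 |
| 50% | 1.25 | 1.25 |
| 55% (6/11) | 1.23 | 1.27 |

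**The case against.** The best defence is that the wider list buys sensitivity. The protocol gives no sensitivity or predictive value for P05 codes, and some true SGA infants may carry only a P07 code. That stands, and it is a real cost of the fix. It does not justify counting every P07 code without regard to gestational age.

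A second defence is that Section 9.2.3 matches the cohorts of women on LMP date and gestational age. The section does not say at what time point gestational age is taken. Even perfect balance on it would leave infants who are not SGA in both numerators, so the dilution and the wrong descriptive proportions would remain.

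A third is that the bias analysis could address outcome misclassification, and a tabulation by code would show the P07 contribution without charts. Both are possible, so it would be too strong to say that the error could not be detected. The protocol commits to neither for SGA.

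A fourth is that at the low end of the assumed range the bias is trivial. That is also fair, and the range above shows it.

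Two further criticisms that a reader might add do not hold. Small term infants above a low-weight cut-off are not lost through the P07 codes: they can be identified by the P05 codes in the same list, so the problem is false positives only. The remark in Section 7.1 that beta-blockers may be linked to growth restriction complicates comparator group A whichever codes are used, and nothing shows that the P07 codes make it worse.

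**Conclusion.** The point holds. Appendix G counts as SGA two code groups that describe absolute weight, against the percentile definition in Sections 4 and 9.3.2.2. Preterm infants who are not SGA can be counted as cases, and the outcome is outside the planned chart validation.

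Under the assumed ranges (8-55% of counted cases not SGA), a true risk ratio of 1.5 would appear as about 1.23-1.46. A risk ratio of 1.5 confined to preterm low birth weight would appear as a false SGA risk ratio of about 1.04-1.27. These figures depend wholly on the assumptions.

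A reader might infer that the outcome would mostly count preterm infants. The documents do not support that: they give no figure, and under most of the assumed combinations such infants are a minority of cases.

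This should be fixed but is not critical. SGA is a secondary outcome, its comparison depends on sufficient sample size and covariate overlap, and the malformation outcome and its sample size are unaffected.

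**What to change.** Define SGA in Appendix G by the P05 codes only. Report low birth weight (P07.0x and P07.1x) as a separate descriptive outcome. If wanted, add a sensitivity analysis that also counts P07-coded infants where gestational-age information supports a weight below the 10th percentile.

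The main change is an edit to the code list. The sensitivity analysis costs more, because it needs a rule linking weight to weeks of gestation.

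The downside is fewer events, and true SGA infants with only a P07 code are missed in the main definition. In the two end scenarios of the second assumption set, that loss is nil when P05 sensitivity is 100%. When P05 sensitivity is 20%, true cases counted fall from 4.88% to 0.10 × 0.2 = 2.0% of infants, while the 5.4% of infants who are false positives are removed.
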